### **2.2.3.3 Rationale for early interception studies predicated on MRD**

Long-term survival can be improved through administration of chemotherapy in the immediate post-operative setting ([Pignon et al 2008](#)), yet chemotherapy in the first-line metastatic setting results in no long-term survival benefit and PFS benefits of only a small number of months ([Cochrane Review 2000](#)). Intervention with consolidation durvalumab following definitive chemoradiation in unresectable stage III NSCLC resulted in improved OS outcomes in an all-comers PD-L1 TPS population ([Antonia et al 2018](#)). Together, these

data highlight that the residual disease left after curative intent therapy is vulnerable to additional adjuvant therapy and thereby provide rationale to escalate this consolidation therapy in these patients in order to intercept relapsing NSCLC when tumor burden is low.

In metastatic NSCLC, the combination of chemotherapy and IO therapy is an established treatment option, particularly in patients whose tumors exhibit PD-L1 TPS <50% and who lack targetable driver mutations (Gandhi et al 2018, Paz-Ares et al 2018). However, this combination leads to an increased rate of treatment discontinuation due to toxicity. For example, in KEYNOTE-407 study, 13.3% of patients treated with chemotherapy and IO therapy discontinued treatment due to toxicity, compared to only 6.4% in the chemotherapy-only arm (Paz-Ares et al 2018). Interception of relapsing NSCLC with maintenance anti-PD-(L)1 monotherapy could improve DFS while sparing patients the toxicity associated with combination treatment for recurrent disease. MRD detection provides a solution to these challenges by facilitating adjuvant studies in smaller, more relevant MRD+ patient populations where adjuvant treatment can be escalated due to the high probability of disease recurrence. Two studies conducted in patients with either NSCLC or urothelial cancer showed that patients treated with durvalumab had a reduction in ctDNA at 6 weeks that was associated with tumor shrinkage and improved PFS and OS (Raja et al 2018). Similar correlation between ctDNA and outcomes have been reported in other studies of agents that target EGFR (Friends of Cancer Research White Paper 2018). These findings suggest that on-treatment ctDNA clearance could be established as a surrogate endpoint of therapeutic response to adjuvant intervention, thereby facilitating accelerated clinical adoption of novel treatment options that prove to be efficacious in this setting.

#### **2.2.3.4 MRD monitoring following surgery and other curative therapy**

In this study, patients will be monitored for MRD over a 96-week surveillance period beginning post-surgery and completion of other curative therapy (complete resection ± neoadjuvant and/or adjuvant therapy). Historic NSCLC adjuvant trials demonstrate that ~75% of the total number of 5-year DFS events occur within the first 2 years following surgery (Wakelee et al 2017, Douillard et al 2006, Waller et al 2004, Arriagada et al 2004). This provides a rationale for 96-week MRD surveillance which should theoretically capture the majority of NSCLC recurrence events.

Tumor doubling times in metastatic solid tumors can be as low as 47 days (reported in colorectal liver metastases) (Wiggans et al 2016). A study of NSCLC brain metastases demonstrated tumor doubling times of 58.5 days (Yoo et al 2008). Since NSCLC tumor burden correlates with concentration of ctDNA in blood (Abbosh et al 2017), it was determined that tumor burden and consequently ctDNA could rise quickly in a relapse setting. Therefore, in order to capture disease recurrence at the lowest possible tumor volume to intervene with durvalumab adjuvant therapy, q6w monitoring using the Sponsor-approved panel for MRD detection will be used.

## 2.3 Benefit/risk assessment

More detailed information about the known and expected benefits and risks and reasonably expected AEs of durvalumab monotherapy may be found in the IB.

See Section 9.6.1 and [Appendix A](#) for information regarding the IDMC.

### 2.3.1 Potential benefits of durvalumab

The majority of the safety and efficacy data currently available for durvalumab are based on the first-in-human, single-agent study **CCI** in patients with advanced solid tumors, the study of durvalumab monotherapy in NSCLC **CCI**, **CCI**, **CCI** and the study of durvalumab monotherapy in NSCLC following completion of platinum-based chemotherapy concurrent with radiation therapy **CCI**. Data from these studies have demonstrated clinical activity of durvalumab therapy in patients with NSCLC. Details pertaining to these studies are provided in the durvalumab IB. Additionally, recent data from D419MC00004 (POSEIDON) show a benefit of durvalumab plus platinum-based chemotherapy in metastatic NSCLC when administered in the first-line setting ([AstraZeneca press release 2019](#); [Johnson et al 2021](#)).

### 2.3.2 Overall risks

Monoclonal antibodies directed against immune checkpoint proteins, such as PD-L1 as well as those directed against PD-1 or CTLA-4, aim to boost endogenous immune responses directed against tumor cells. By stimulating the immune system, however, there is the potential for adverse effects on normal tissues.

Most adverse drug reactions seen with the immune checkpoint inhibitor class of agents are thought to be due to the effects of inflammatory cells on specific tissues. These risks are generally events with a potential inflammatory or immune-mediated mechanism and that may require more frequent monitoring and/or unique interventions such as immunosuppressants and/or endocrine therapy. These immune-mediated effects can occur in nearly any organ system and are most commonly seen as gastrointestinal AEs such as colitis and diarrhea, pneumonitis/interstitial lung disease (ILD), hepatic AEs such as liver enzyme elevations, skin events such as rash and dermatitis, and endocrinopathies including hypo- and hyper-thyroidism.

#### 2.3.2.1 Durvalumab

Risks with durvalumab include, but are not limited to, diarrhea/colitis, pneumonitis/ILD, endocrinopathies (ie, events of hypophysitis/hypopituitarism, adrenal insufficiency, hyper- and hypo-thyroidism, type I diabetes mellitus, and diabetes insipidus), hepatitis/increases in transaminases, nephritis/increases in creatinine, rash/dermatitis, myocarditis, myositis/polymyositis, infusion-related reactions, hypersensitivity reactions, pancreatitis, serious infections, and other rare or less frequent inflammatory events including neuromuscular toxicities (eg, Guillain-Barre syndrome, myasthenia gravis).

For information on all identified and potential risks with durvalumab, please always refer to the current version of the durvalumab IB.

In monotherapy clinical studies, including a study in unresectable NSCLC in which patients received durvalumab following concurrent SoC platinum-based chemoradiotherapy (PACIFIC), AEs at an incidence of  $\geq 20\%$  include events such as fatigue, cough, decreased appetite, dyspnea, and nausea. Approximately 10% of patients discontinued the drug due to an AE. Please see the current version of the IB for a detailed summary of the monotherapy data including AEs, SAEs), and Common Terminology Criteria for Adverse Events (CTCAE) Grade 3 to 5 events reported across the durvalumab program.

The majority of treatment-related AEs were manageable, with dose delays, symptomatic treatment, and in the case of events suspected to have an immune basis, the use of established treatment guidelines for immune-mediated toxicity (see Section 8.4.5).

A detailed summary of durvalumab monotherapy AE data can be found in the current version of the durvalumab IB.

### **2.3.3 Overall benefit/risk**

Recent progress in immunotherapy for NSCLC has been a substantive advance, although further improvement is needed. However, up to 60% of patients will still experience disease recurrence. Novel treatment approaches are needed to improve the long-term prognosis for patients with early-stage NSCLC. Identification of patients who will benefit from immunotherapy in the adjuvant setting following curative intent therapy could lead to improved outcomes. Early studies of immunotherapy in the neoadjuvant setting in patients with resected NSCLC have shown promising clinical activity as well as acceptable safety profiles (Forde et al 2018; Shu et al 2018). Data from PACIFIC demonstrated the efficacy and tolerability of durvalumab administered after completion of platinum-based adjuvant chemotherapy (Antonia et al 2018). Therefore, in this Phase III study, the administration of durvalumab monotherapy compared to placebo will be investigated in patients with stage II-III NSCLC who are or become MRD+ following curative intent therapy.

The study design aims to minimize potential risks. For example, a safety evaluation by an IDMC will take place to assess whether durvalumab may adversely impact post-operative or post-treatment outcomes; the IDMC will report back to the Sponsor.

Therefore, based upon the available nonclinical and clinical safety data and the mitigations designed for this study, the investigation of the potential therapeutic efficacy and safety of durvalumab monotherapy following completion of curative intent therapy is acceptable in patients with completely resected NSCLC and the overall benefit/risk assessment supports the proposed study design.

***Note for CSP v2.0: There is no change to the overall benefit/risk assessment of the study.***

### 3 OBJECTIVES AND ENDPOINTS

*From CSP v2.0 implementation at site, please use Section 10 as a reference point for the study. This study has closed enrolment early and patients will either start open-label durvalumab or be discontinued from the study.*

*The objectives and endpoints have been updated for CSP v2.0. All analyses of the objectives and endpoints will be descriptive only and considered exploratory. Please see Section 10.4 for additional information.*

**Table 7 Study objectives and endpoints/variables**

Primary objective:	Endpoint/variable:
To assess the efficacy of durvalumab compared to placebo as measured by DFS in all randomized patients	DFS in FAS (using Investigator assessments according to RECIST 1.1)
Secondary/safety objective:	Endpoint/variable:
To assess the safety and tolerability profile of durvalumab monotherapy compared with placebo	AEs, physical examinations, vital signs, and laboratory findings
Exploratory objectives:	Endpoint/variable:
To assess the efficacy of durvalumab compared to placebo as measured by DFS in the PD-L1 TC $\geq$ 1% analysis set	DFS in PD-L1 TC $\geq$ 1% (using Investigator assessments according to RECIST 1.1)
To assess the efficacy of durvalumab compared to placebo on post-recurrence outcomes	PFS (using local standard practice) CCI [REDACTED] CCI [REDACTED]
To assess the efficacy of durvalumab compared to placebo as measured by OS in the PD-L1 TC $\geq$ 1% analysis set and in all randomized patients	OS in PD-L1 TC $\geq$ 1% and in FAS
To assess patient-reported symptoms, functioning, and HRQoL in patients treated with durvalumab compared to placebo	Change from baseline and time to deterioration in EORTC QLQ-C30 and EORTC QLQ-LC13
To investigate the relationship between a patient's baseline PD-L1 TC expression and efficacy of study treatments	IHC analysis of PD-L1 TC expression and spatial distribution within the tumor microenvironment relative to efficacy outcomes (ie, DFS, OS)
To assess the efficacy of durvalumab monotherapy to clear ctDNA compared to placebo	ctDNA endpoints, as defined by: 
 
• Best overall clearance rate (number converted at any time)
 
• Best confirmed clearance rate (as above but confirmed at subsequent visit)
 
• Time to ctDNA clearance
 
• Duration of ctDNA clearance
 
• Time to ctDNA recurrence
 
• Time to confirmed ctDNA recurrence
 
• Changes in variant allele frequencies (VAF) following treatment
 

To assess the relationship between treatment effect on DFS and treatment effect on ctDNA endpoints	ctDNA endpoints (as defined above) and DFS

**Table 7 Study objectives and endpoints/variables**

To assess the association of TMB with efficacy of durvalumab compared with placebo, and other biomarker subpopulations	DFS, OS, and other efficacy endpoints in patients according to TMB in subpopulations including, but not limited to, PD-L1 TC $\geq$ 1%, ctDNA endpoints, etc.
To investigate biomarkers in tumor and periphery at baseline, on treatment, post-treatment and/or at recurrence wherever feasible to identify markers related to disease, mechanism of action of the drug and/or their associations with response and clinical endpoints.	Exploratory markers, which may include, but are not limited to: tumor, immune, and/or stromal cell gene and protein expression profiles within the peripheral and tumoral compartments. TMB and somatic mutations in tissue and/or blood/plasma. Changes in RNA, DNA or protein Attributes of tumor microenvironment that could be assessed using various methods which may include, but not limited to, high content imaging, multiplex RNA/DNA/protein analysis with spatial resolution such as Mass Spec or other technologies.
To evaluate patient-reported treatment-related symptoms using PRO-CTCAE To assess the patient’s global impression of symptoms severity, and global treatment tolerability	Pre-specified items on the PRO-CTCAE Patient global assessments
To explore the impact of treatment and disease	CCI, descriptor, and VAS
To assess alternative methodologies for determining MRD	MRD determinations in screened patients
To assess prognostic value of ctDNA quantification at baseline	ctDNA quantification vs binary MRD classification (+/-) to DFS and other efficacy endpoints
To assess prognostic value of MRD classification by comparing outcomes of randomized (MRD+) placebo-treated patients to those of patients in surveillance and/or observation	
 
MRD status as determined at screening and various timepoints post-surgery/curative intent therapy
 
DFS and other efficacy endpoints
 
Time from surgery to DFS
 
Site of relapse
 
Second primary NSCLC
 

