Based on internal Sponsor data from stage II-III resected patients, it is estimated that **CC1** of randomized patients will be PD-L1 TC≥1%. To ensure that the target of **CC1** PD-L1 TC≥1% patients are randomized in the study, enrollment of PD-L1 TC<1% patients into surveillance will end once **CC1** PD-L1 TC<1% patients have been randomized. The remaining PD-L1 TC<1% patients will be immediately withdrawn from surveillance. Additional data will not be collected on these patients. Patients who are determined to be PD-L1 TC<1% during the first screening will not be eligible to continue to surveillance

and will be considered screen failures (see Section 5.5). Please note that any PD-L1 TC <1% patient who is already in the observation arm will remain in the study.

Similarly, enrollment into the study will end once 284 MRD+ patients are randomized. Patients in surveillance will be immediately withdrawn from the study and additional data will not be collected on these patients. Please note that patients already in the observation arm will remain in the study.

**Note:** In the event the Sponsor withdraws patients from surveillance because the applicable cohort(s) have been filled, these patients may continue to receive CT scans every 12 weeks until 96 weeks have elapsed (relative to the start of surveillance) to honor the patient's consent to q12w scans or until disease recurrence or primary DFS analysis (whichever occurs first). No additional data will be collected on these patients.

Up to 142 of the patients who complete their 96-week surveillance period, remain MRD-, and have no evidence of RECIST 1.1-defined disease recurrence may be eligible for entry into an observation period initiated by the signing of a separate informed consent (ICF2b; Table 4). These patients will be followed for SAEs, DFS, OS, subsequent anticancer therapy, and MRD assessments for 24 months or until completion of the study (whichever occurs first). Patients who complete 24 months of observation will be followed for OS until the end of the study. Data from this cohort of patients will be compared to the patients randomized to placebo to support the hypothesis that MRD can be used as a prognostic biomarker to identify patients at high risk of disease recurrence prior to radiologic evidence of disease.

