## 5 STUDY POPULATION

*Note for CSP v2.0: Enrolment is closed as of 25May2022 and no patients will be randomized following implementation of this amendment at site.*

*Section 5.3 remains in effect for the patients who receive durvalumab during open-label or double-blind treatment and up to 90 days after the last dose.*

Prospective approval of protocol deviations to recruitment and enrollment criteria, also known as protocol waivers or exemptions, is not permitted.

Each subject should meet all of the inclusion criteria and none of the exclusion criteria for this study in order to be randomized to a study intervention. Under no circumstances can there be exceptions to this rule. Subjects who do not meet the entry requirements are screen failures, refer to Section 5.5.

In this protocol:

- “**Enrolled**” patients are defined as those who sign ICF1.
- “**Patients in surveillance**” are defined as those who have successfully completed the first screening and have had at least one plasma sample collected for MRD testing but are not randomized nor in observation.
- “**Randomized**” patients are defined as those who sign ICF2a, complete the second screening period, undergo randomization, and receive a randomization number.

- “**Patients in observation**” are MRD- patients who remain MRD- during their 96-week surveillance period and who have no evidence of RECIST 1.1-defined disease recurrence. These patients have signed ICF2b and entered the observation cohort.

For procedures for withdrawal of incorrectly enrolled subjects see Section 6.2.2 and Section 7.3.

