## 5.5 Screen failures

Screen failures are patients who do not fulfill the eligibility criteria for the study, and therefore must not enter the surveillance period (if eligibility during the first screening is not met) or must not be randomized (if eligibility during the second screening is not met). These patients should have the reason for study withdrawal recorded as "eligibility criteria not fulfilled" (ie, patient does not meet the required inclusion/exclusion criteria). This reason for study withdrawal is only valid for screen failures (ie, not randomized patients). Patients may not be rescreened or re-randomized in this study. The reason for screen failures will be captured in the appropriate section of the electronic case report form (eCRF).

A minimal set of screen failure information is required to ensure transparent reporting of screen failure patients to meet the Consolidated Standards of Reporting Trials (CONSORT) publishing requirements and to respond to queries from regulatory authorities. Minimal information includes demography, screen failure details, eligibility criteria, and any SAE. In addition, surgical history, scans and imaging data, and the date of disease recurrence will also be collected on screen failed patients.

See [Table 1](#) in the SoAs and [Section 8.2.2](#) for additional details on information that should be collected for patients who participate in the first screening period and surveillance of this study (initiated by signing ICF1).

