#### **9.4.1.2 Primary endpoint: disease-free survival**

DFS is defined as the time from the date of randomization until the date of disease recurrence (local, regional, or distant disease recurrence or second primary NSCLC) using Investigator assessments according to RECIST 1.1, or date of death due to any cause, whichever occurs first.

Patients who are disease-free, ie, have not experienced disease recurrence, and alive at the time of analysis will be censored at the latest date of assessment from their last evaluable RECIST 1.1 assessment. However, if the patient experiences disease recurrence or dies after 2 or more missed visits, the patient will be censored at the latest evaluable RECIST 1.1 assessment prior to the 2 missed visits. If the patient has no evaluable assessments or does not have baseline data, they will be censored at Day 1 unless they die within 2 visits of baseline, then they will be treated as an event with the date of death as the event date. The primary endpoint analysis of DFS will be based on Investigator RECIST 1.1 assessments.

The DFS time will always be based on scan/assessment dates and not visit dates.

DFS rate at 6 and 12 months is defined as the proportion of patients alive and disease-free at 6 and 12 months respectively, estimated from Kaplan-Meier plots of the primary endpoint of DFS.

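### The exploratory MRD-prognosis comparison groups patients by later randomization, not by MRD status over time, so any clock that starts before randomization credits placebo patients with event-free time

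*Protocol*

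**What the plan says.** The objective stands in protocol Section 3, Table 7, and in the synopsis (Section 1.2). It assesses the prognostic value of MRD classification by "comparing outcomes of randomized (MRD+) placebo-treated patients to those of patients in surveillance and/or observation". The same row lists as variables "MRD status as determined at screening and various timepoints post-surgery/curative intent therapy", DFS with other efficacy endpoints, and "Time from surgery to DFS".

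Section 5 defines the groups. Patients in surveillance have passed the first screening and "have had at least one plasma sample collected for MRD testing but are not randomized nor in observation". Patients in observation "are MRD- patients who remain MRD- during their 96-week surveillance period and who have no evidence of RECIST 1.1-defined disease recurrence". Inclusion criterion 14 requires a recent scan free of recurrence before randomization, and Section 5.5 says that patients "must not be randomized (if eligibility during the second screening is not met".

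On the clock, Section 9.4.1.2 says: "DFS is defined as the time from the date of randomization until the date of disease recurrence". It gives no starting date for patients who are never randomized.

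Section 4.1, marked as describing the original design, says of the observation cohort: "Data from this cohort of patients will be compared to the patients randomized to placebo to support the hypothesis" that MRD is prognostic.

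After early closure all analyses are descriptive and exploratory (protocol Sections 3 and 10.4). SAP Section 1.2 expects about 30 randomized patients and no entry to observation once v2.0 is in force. SAP Section 4.3 limits CSR listings of surveillance data to the FAS but allows further exploratory work. SAP Sections 1.1.3, 3.4, 4.2.7 and 4.2.8 are wholly or largely redacted.

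**The concern.** Each label is fixed by later events. To be a placebo patient, someone must become MRD+, have a clean scan and reach randomization without recurring. Measured from surgery or from the start of surveillance, all of that time is event-free by construction, yet it counts as follow-up in the MRD+ group. Patients whose disease recurs first stay on the other side. This immortal time pulls the MRD+ event rate down and understates the effect that the objective is meant to show. An observation patient, by contrast, carries 96 event-free weeks by selection, which biases the other way.

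A descriptive Kaplan-Meier curve or median from surgery carries the same bias as a formal test. At stake is how well this study can support its own premise that MRD picks out high-risk patients.

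**Working it through.** **Plan's own figure.** The documents give no sample size, event count or effect size for this objective, so there is nothing to reproduce. The checks below are illustrations.

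**Model A, truncated follow-up.** From the protocol: 22% MRD+ over 96 weeks (Section 1.2), with exponential emergence (Section 4.1.1). 96 weeks = 96 × 7 / 30.44 = 22.08 months, so the emergence rate is -ln(0.78) / 22.08 = 0.0113 per month. Assumed: constant event hazard of 0.008 per month while MRD-, multiplied by the true HR once MRD+; randomization one month after MRD+ if still event-free; follow-up uniform to 17 months. Randomized patients carry the untreated hazard, as placebo patients would.

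Naive ratio = (events / person-months, randomized) / (events / person-months, not randomized), all counted from the first surveillance sample. Ranges are over repeat runs.

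| True HR | Naive, from first sample | Placebo clock from randomization | MRD time-varying |
|---|---|---|---|
| 1 | 0.42 to 0.44 | about 0.9 | 0.97 |
| 3 | 1.21 to 1.27 | about 2.7 | 2.97 |
| 5 | 1.91 to 2.03 | 4.5 to 4.7 | 5.14 |
| 10 | 3.45 to 3.52 | about 8.7 | 10.25 |

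The first two result columns have the same events and differ only in placebo person-time. At a true HR of 1, 0.44 / 0.92 = 0.48, so about half of the placebo person-time in the naive ratio lies before randomization.

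**Model B, long follow-up, true HR of 1.** From the protocol: 22% MRD+, 96 weeks, six-weekly sampling, and 5-year DFS of about 40% (varied from 30% to 50%). Assumed: constant hazards, 28 days to randomization, 14% of otherwise eligible MRD+ patients not randomized, 46 months of follow-up, observation cohort not capped at 142. Cox hazard ratios, clock from the start of surveillance:

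- placebo versus all non-randomized: 0.61 to 0.67
- placebo versus observation only: 1.43 to 1.63
- placebo clock from randomization, comparator from surveillance start: 0.85 to 0.94
- time-varying MRD: 0.98 to 1.03

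The sign of the bias therefore depends on which comparator the and/or in the objective selects.

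**Unrandomized MRD+ patients in the comparator.** On the original numbers, 22% × 1500 = 330, and 330 - 284 = 46. The non-randomized number 1500 - 284 = 1216, and 46 / 1216 = 3.8%. At 20% prevalence the excess is 300 - 284 = 16, or 1.3%. At or below 284 / 1500 = 18.9% it is nil. Model A gives 1% to 2%. After closure, 22% × 416 - 30 is about 61, but that is only a ceiling: surveillance was cut short, and not everyone who consented entered it.

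**The case against.** Four points on the other side carry weight.

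- **The clock.** A reader might infer that no choice of clock rescues the comparison. That is too strong. With constant hazards, the protocol's own DFS origin removes most of the bias against surveillance patients, as the third column of the table shows. It does not serve the surgery-origin endpoint, leaves the comparator without a stated origin, and weakens if hazards change over time.
- **MRD+ patients in the comparator.** A reader might infer that they swamp it. They do not: the share is about 1% to 4%. It also rests on the wording of the Section 5 definition. Table 1 ends surveillance when MRD emerges, and recurrence during surveillance makes a patient a screen failure.
- **The observation cohort.** A reader might infer that the effect will be overstated against it. That is now largely moot, because no patients enter observation after v2.0 and Section 10 makes no provision for such a group.
- **A method may exist.** Serial MRD status is already a listed variable, an objective is not an estimator, and exploratory biomarker analyses go to a separate plan (protocol Sections 8.7.3 and 9.5.6). With the SAP's exploratory text redacted, the documents do not support saying that no suitable method was planned.

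The Model A hazard can also be questioned. It implies 5-year DFS of exp(-0.008 × 60) = 62%, against about 40% in the protocol; Model B covers 30% to 50%. The plan's 4-month placebo median gives ln 2 / 4 = 0.173 per month, about 22 times 0.008. Even then the naive ratio is 5.7, so MRD would still look adverse, though far less than it is.

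**Conclusion.** The point holds in a limited form, at low severity. As Table 7 states it, the comparison sorts patients by later randomization. With the surgery-origin endpoint, or any origin before randomization, that understates MRD's prognostic effect against surveillance patients. In Model A a true ratio of 5 shows as about 2 and a true ratio of 10 as about 3.5; a null effect shows as about 0.4 in Model A and 0.61 to 0.67 in Model B. These sizes rest on constant hazards and the assumed lags and follow-up. The direction assumes that patients who recur during surveillance stay in the comparator, as the Section 5 definition reads.

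The handling of never-randomized MRD+ patients is a secondary, small ambiguity. Practical impact is limited by about 30 randomized patients, roughly half of them on placebo, and by descriptive reporting.

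**What to change.** In Table 7 and the exploratory analysis plan, define the comparison among all patients with a surveillance MRD result:

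- time zero at the first surveillance plasma sample;
- MRD status as a time-varying covariate that turns positive on the collection date of the first positive sample, whether or not the patient is later randomized;
- durvalumab patients censored at randomization;
- a supporting landmark comparison by first-sample MRD result.

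This also settles where never-randomized MRD+ patients belong.

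The cost is wording and modest programming, since serial MRD results are already listed. Three limits remain. Intervals will be wide, because few untreated MRD+ patients exist. Follow-up of non-randomized patients stops when they are discontinued, and Table 17 does not explicitly list a recurrence date for them, although Table 1 and Section 5.5 require it for screen failures; completeness should be checked first. Results stay descriptive. If the redacted text or the separate biomarker plan already contains such a method, only the Table 7 wording needs aligning.
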